15.2. Storage of Study Devices at Investigational Center

Study devices are to be stored in a secure environment with access limited to authorized research personnel. Study devices are to be stored in the proper environmental conditions, as identified in the user guide/labeling.

15.3. Disbursement of Study Devices

Each time a study device is disbursed to a Subject by the Investigator or authorized member of the research team, all required eCRF and source documentation will be completed. Documentation may include:

- Date of disbursement

- Subject ID
- Lot number(s)
- Serial Number
- Reference Number
- Amount dispensed

15.4. Return or Disposal of Study Devices

After use by the subject, the investigational center is expected to accept and retain all devices as described in Table 1; and store them in a secure environment. If containers/units/devices are missing, document the reasons in the eCRF. If discrepancies between amounts used by subjects and amounts expected to be returned exist, document the reasons in the eCRF.

The study devices required to be accounted, as described in Table 1, will be returned by subjects to the investigational center and then to the Sponsor. Serialized devices provided to the investigational center may be returned as subjects complete the study, at the end of study or upon sponsor request. The quantity received by the investigational center and the quantity returned to sponsor should be equal. The investigational center will provide details of the disposition of all unreturned serialized devices (excluding the Study Meter and Ketone Meter) in the eCRF.

Used glucose sensors are not expected to be returned by subjects to the investigational center and therefore are not expected to be returned to the sponsor. Other unused consumable devices (i.e., infusion sets, alcohol wipes, Study Meter supplies, overtape, etc.), supplies or materials may be returned to the sponsor or retained by investigational center for educational purposes only, or may be disposed of properly by the investigational center staff.

Disposable devices and supplies that have been **used** by a subject will be disposed of properly by the subject or the investigational center staff during the conduct of the study. This would include glucose sensors, meter testing strips and supplies, infusion sets and adhesive overtape.

All study devices that were required to be entered into the study database are required to be accounted for as described herein prior to return to sponsor or at the end of the study.

The Sponsor will provide study subjects with an opportunity to participate in a transition program for the 670G pump and the Guardian Link Transmitter. The 670G transition program applies only to the FDA approved age group, 7years and older, in US.

16. Safety

16.1. Adverse Event

The Medtronic Clinical Research Department, in conjunction with the Regulatory Affairs Department, in Northridge, California will monitor and manage adverse event reporting for the study and determine whether the event requires reporting to regulatory agencies. The sponsor will ensure timely Adverse Event reporting to meet regulatory requirements.

Throughout the course of the study, investigational centers will make all efforts to remain alert to possible reportable adverse events or untoward findings. The study personnel will elicit reports of adverse events from the subject at each visit (including phone calls) documenting the medical diagnosis, date of event start and end, severity, causality (relationship to device or procedure), treatment, resolution and description that includes the details of the event.

16.2. Reporting of Adverse Events

The Investigator or designee will record ALL adverse events while the Subject is enrolled in the clinical study. This includes AE that are device or study procedure related as well as those events with no relationship to the study. Examples include:

- Device related (ADE): insertion site infection
- Serious adverse device effect: cellulitis at device insertion site requiring hospitalization
- Procedure related AE: bruising at IV insertion site
- Not related to study: cold, flu, appendicitis

Adverse events will be documented in the subject source file and reported to Sponsor on an eCRF. The investigational center is responsible for documentation of adverse events including obtaining source documents related to the event, such as emergency medical technician/paramedic reports, hospital records (admission summary; lab results, test results, discharge summary) or device uploads to support the event. Source documents will be reviewed to determine if additional adverse events have occurred and require reporting.

Narratives gathered from completed questionnaires will not provide the basis of an adverse event report however could lead to discussions that result in the identification of a reportable AE.

Adverse events that have not resolved at the time of the subject's discontinuation or completion of the study will be documented as ongoing at study end in subject source and on an eCRF. The Investigator should ensure that subject is aware of any follow-up or additional treatment that is required for any ongoing AE at end of study participation; however, there will be no eCRF entry for the ongoing follow-up.

16.3. Notification of Adverse Events

Within 24 hours of investigator or study coordinator awareness, the investigational center staff must report all Severe Hypoglycemia; DKA; Serious Adverse Events; Serious Adverse Device Effects, Unanticipated Serious Adverse Device Effects and any Unanticipated Adverse Device Effect to Medtronic. Regulatory authorities should be notified per local requirements. The AE eCRF will be completed with all known details within 24 hours of investigational center awareness – this will serve as notification to Medtronic. If the study database cannot be accessed due to technical problems, contact the Sponsor via email at [contact] and provide the known details of the event. Once the access issue has been corrected the event should be entered onto an AE eCRF. All other reportable adverse events should be entered on the eCRF within 14 days of subject report to the investigational center.

16.4. Expedited Safety Reporting Requirements

For device studies, investigators are required to submit a report of a UADE to the sponsor and the reviewing IRB/EC as soon as possible, but in no event later than 10 working days after the investigator first learns of the event (21 CFR 812.150(a)(1)).

The Sponsor will notify the investigator and IRB/EC of any event that results in a safety report to the FDA/local regulatory authority within EMEA. Documentation of IRB/EC notification of any safety event must be kept at the investigational center and a copy sent to the Sponsor.

It is the responsibility of the investigator to follow their IRB/EC and regulatory authority reporting requirements.

16.5. Reporting of Glycemic Events

1. **Severe Hypoglycemia** is an event requiring assistance of another person due to altered consciousness to actively administer carbohydrate, glucagon, or other resuscitative actions. This means that the subject was impaired cognitively to the point that he/she was unable to treat his or her self, was unable to verbalize his or her needs, and was incoherent, disoriented and/or combative.

These episodes may be associated with sufficient neuroglycopenia to induce seizure or coma. Plasma glucose measurements may not be available during such an event, but neurological recovery attributable to the restoration of plasma glucose to normal is considered sufficient evidence that the event was induced by a low plasma glucose concentration. **(Adapted from American Diabetes Association Workgroup on Hypoglycemia, Diabetes Care 28:1245-1249, 2005)**

2. **Diabetic Ketoacidosis/DKA diagnostic criteria:** blood glucose greater than 250 mg/dL (or greater than 13.9 mmol/L), arterial pH less than 7.3, bicarbonate less than 15mEq/l, moderate ketonuria or ketonemia and requiring treatment within a health care facility. **(American Diabetes Association-Diabetes Care, Volume 27, Supplement 1, January 2004; S94-S102)**

Hyperglycemic events will be recorded as an adverse event if the event involved DKA with the presence of all of the following:

- Symptoms such as polyuria, polydipsia, nausea, or vomiting
- Serum ketones or large/moderate urine ketones
- Arterial blood pH less than 7.30 or serum bicarbonate less than 15mEq/l
- Treatment provided in a health care facility

3. **Severe Hyperglycemia** is defined as hyperglycemia (blood glucose >300 mg/dL) with blood glucose ketones >0.6mmol/L or accompanied by symptoms of nausea, vomiting or abdominal pain.

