16.9. Severity of Event (Intensity)

A clinical determination of the intensity of the event will be made. The following guidelines should be used:

- **Mild:** transient, needing no special treatment, and/or does not interfere with the subject's daily activity.
- **Moderate:** low level of inconvenience or concern to the subject and may interfere with daily activities, but is usually improved by simple therapeutic remedy.
- **Severe*:** interrupts a subject's daily activity and typically requires intervening treatment.

*Please Note: In the classification of adverse events, the term “**severe**” is not the same as “**serious**.” The term “**severe**” relates to an indication of the intensity of a specific event (as in mild, moderate, or severe chest pain). The term “**serious**” relates to a participant/event outcome or action criteria, usually associated with events that pose a threat to a participant's life or functioning.

17. Data Safety Monitoring Board

A DSMB consisting of external physicians with an expertise in Endocrinology and the management of insulin requiring diabetes including CGM, along with an external statistician will be convened to review study progress, endpoints and safety.

The DSMB will perform a number of functions:

1. Adjudication of the following events:

- Serious Adverse Event
- Serious Adverse Device Effect
- Unanticipated Adverse Device Effect
- Severe Hypoglycemia

- Diabetic Ketoacidosis

The DSMB will assess these events to determine agreement or disagreement with the Investigator classification of the event. The Sponsor will notify the Investigator of any disagreement in assessment of an event by the DSMB. The DSMB will meet a minimum of every 6 weeks to adjudicate these events unless there are no events to adjudicate.

2. DSMB will track and trend the overall Safety of the study.

Incidence for the following will be reviewed by the DSMB:

- Incidence of all SAEs.
- Incidence of severe hypoglycemia
- Incidence of DKA
- Incidence of device related adverse events.

Applicable information for device related adverse events may include:

- Whether or not the event was unanticipated
- Review of sensor data from CareLink report (when applicable)
- Review of pump data from CareLink report (when applicable)
- Misuse of the device by the user

3. The DSMB will meet sooner if there is a DKA event, a UADE or a severe hypoglycemia event as outlined in the stopping rules for the entire study:

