- DSMB is to review the event within 48 hours from the time that the sponsor is notified. If possible, the investigator should be available to answer questions by DSMB.
- DSMB will recommend a decision to the sponsor on the following:
 - Whether or not enrollment will continue to be on hold
 - Whether or not the entire study will need to be stopped including for those subjects who have received study devices already.

4. The DSMB will provide a recommendation to the sponsor on whether or not pediatric subjects 2-4 years of age will be permitted to enroll into the study. The recommendation is based on a review of data from 10 subjects 5-6 years of age after they have completed the first month of the study period.

General guidance for DSMB's recommendations to sponsor should be based on the following:

Review of events may require the following information. Final disposition of an event may be delayed based on obtaining this information:

- Monitoring by sponsor at site
- Device return and failure analysis
- Carelink upload and review of Carelink reports
- Subject clarification to site regarding details about the event
- Source documents that support event: Paramedic records; ER records; Lab records; Hospital admission and discharge summary

The following factors should be carefully considered in the DSMB's recommendation to sponsor:

1. Was the severe hypoglycemia or DKA related to the HCL algorithm, SmartGuard with predictive threshold suspend or was it related to a known insulin pump risk? For example, a question that may

be considered in DKA would be whether the event was related to an infusion set issue or caused by the HCL algorithm.

2. Another important consideration would be if the severe hypoglycemia or DKA event was related to a device malfunction versus patient non-compliance. For example, if a software anomaly leading to an under-delivery of insulin is discovered versus the subject repeatedly ignoring alarms prompting the subject to take action.
3. Severe hypoglycemia or DKA caused directly by an infusion set issue when the study pump is functioning as intended would likely result in acceptance to proceed with the study versus severe hypoglycemia or DKA that are directly caused by the HCL algorithm or a device malfunction might stop study enrollment or entire study altogether.

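### Section 18 would withdraw subjects for sensor wear that Section 11.3 instructs, and Section 16.5 ties recording of DKA to a symptom condition that its own diagnostic criteria lack (minor)

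*Protocol*

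**What the plan says.** **Sensor wear.** Section 18 gives a list of events after which a subject is to be withdrawn. One is persistent wear of a sensor past a labelled limit of 6 days. Footnote 8 to the tables in Section 11.3 tells subjects to change the sensor at 7 days, on the pump's expiry alert, or sooner if events require it.

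**DKA.** Section 16.5 first states the diagnostic criteria: blood glucose above 250 mg/dL, then "arterial pH less than 7.3, bicarbonate less than 15mEq/l, moderate ketonuria or ketonemia and requiring treatment within a health care facility". Symptoms are not among them. It continues: "Hyperglycemic events will be recorded as an adverse event if the event involved DKA with the presence of all of the following". The list under that sentence begins with "Symptoms such as polyuria, polydipsia, nausea, or vomiting", includes "Arterial blood pH less than 7.30 or serum bicarbonate less than 15mEq/l", and also asks for ketones and treatment in a health care facility. Elsewhere, Section 16.2 says "The Investigator or designee will record ALL adverse events while the Subject is enrolled in the clinical study", and Section 16.3 says that, within 24 hours of awareness, "the investigational center staff must report all Severe Hypoglycemia; DKA; Serious Adverse Events" and further event types to the sponsor, with the completed adverse event eCRF serving as the notice. Section 16.6 counts abnormal laboratory results as adverse events.

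**Severe hypoglycemia.** The Section 18 list includes a severe hypoglycemic episode without qualification. Section 19.1 and the synopsis stop a subject for severe hypoglycemia that follows from the subject's non-compliance or from other safety concerns about that individual. For DKA, the same section applies to every event.

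**The concern.** The purpose of this single-arm study is to show that the system is safe. Sites apply the withdrawal and event-recording rules directly from the protocol, so each rule should have one reading.

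The sensor rule is the clearest fault: compliance with one section meets a withdrawal criterion in another. A site that applies Section 18 as written could remove compliant children, and a site that ignores it departs from the protocol.

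For DKA, the recording rule is narrower than the definition it rests on. DKA incidence is a summarized safety outcome. A DKA also withdraws the subject (Sections 18 and 19.1), pauses enrollment pending DSMB review (Section 19.2) and is compared with a DSMB reference count (Section 17). A condition that is absent from the diagnosis should not stand between a diagnosed event and its entry as DKA.

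For severe hypoglycemia, the two lists differ in width, so sites may handle the same event differently. Only retention is affected.

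**Working it through.** The plan gives no figure on this point to reproduce. The check compares the texts and adds simple arithmetic.

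**1. Sensor wear.** Inputs: 6-day limit (Section 18), 7-day replacement (Section 11.3, footnote 8), study period of 96 to 110 days (Section 8.2).

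- Excess per full wear: 7 − 6 = 1 day.
- Full 7-day wears in 96 days: floor(96/7) = 13, covering 13 × 7 = 91 days.
- Full 7-day wears in 110 days: floor(110/7) = 15, covering 15 × 7 = 105 days.

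A subject who always wears each sensor to the alert exceeds the limit 13 to 15 times, which can fairly be called persistent. This is an upper figure, because sensors may be changed early.

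**2. DKA.** Let G = glucose above 250 mg/dL, P = pH below 7.3, B = bicarbonate below 15, S = symptoms, K = ketones and T = facility treatment. Hold K and T present and treat K as the same in both places, although the wording differs slightly.

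- Diagnostic criteria, with the comma list read as all required: G and P and B.
- Recording list taken alone: S and (P or B).

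The four remaining items give 2 × 2 × 2 × 2 = 16 combinations:

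| Outcome | Combinations |
|---|---|
| Both met (G, P, B, S) | 1 |
| Diagnostic criteria only (G, P, B, no S) | 1 |
| List only (S, with P or B, but not all of G, P, B) | 5 |
| Neither | 9 |

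These are logical cases, not frequencies. The documents give no rate for any of them.

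The lead-in to the list presupposes that the event involved DKA, so the natural reading is that the diagnostic criteria and the list must both hold. The five list-only cases are then not DKA, and the choice between pH and bicarbonate in the list has no effect. One discrepancy remains: an event that meets every diagnostic criterion without symptoms, for example glucose 300 mg/dL, pH 7.2, bicarbonate 12, ketones and facility treatment. Section 16.5 would not enter it as an adverse event, whereas Sections 16.2, 16.3 and 16.6 would.

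**3. Severe hypoglycemia.** Section 18 covers every episode; Section 19.1 and the synopsis cover a subset. Section 19.1 treats DKA without qualification and severe hypoglycemia with one, so the qualifier looks intended, yet the wider rule in Section 18 leaves it without effect.

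**The case against.** The strongest reply is that nothing is lost in practice. Section 16.3 is unconditional for DKA and uses the adverse event eCRF as its vehicle, so a symptom-free DKA reaches that form anyway. The symptom item is open-ended, and a child this acidotic under facility treatment will rarely have no symptom at all. Section 17 adds that "The DSMB will assess these events to determine agreement or disagreement with the Investigator classification of the event", and the material the DSMB may call for includes "Source documents that support event: Paramedic records; ER records; Lab records; Hospital admission and discharge summary". This stands, and it keeps the point minor. It does not make the wording of Section 16.5 correct: the DSMB works on events that sites have reported, and the condition still contradicts three neighbouring sections.

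A reader might infer that symptom-free DKA would go unrecorded, or that the protocol has two rival definitions of DKA. The documents support neither. Section 16.3 closes the recording gap, and only one set is labelled diagnostic.

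On sensor wear, Section 18 appeals to the label, which is not among the documents, and the word for persistence leaves the site some judgement. Both remarks are fair. The direction of the correction therefore rests on the expiry alert in footnote 8 and needs checking against the label. The mismatch itself does not depend on the label.

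On severe hypoglycemia, Section 19.1 does not say that its cases are the only ones, and withdrawing the subject satisfies both sections. This is an overlap of unequal rules, not a strict contradiction. The advice in footnote 5 of Section 11.3 to switch Auto Mode off after an episode does not show that the subject was meant to stay, because the same advice is given for DKA, where withdrawal is not in doubt.

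**Conclusion.** The point holds as a minor one, in three parts of unequal weight.

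- **Sensor wear** is a definite conflict: 1 day per full wear, at most 13 to 15 wears per subject, assuming continuous wear to the expiry alert. No effect on an endpoint or on safety is shown.
- **DKA recording** carries one surplus condition. It conflicts with Sections 16.2, 16.3 and 16.6, but its practical effect is small because Section 16.3 already captures the event. No frequency is claimed.
- **Severe hypoglycemia** is a drafting inconsistency that affects retention only. A reader might divide the DSMB reference count of 4 subjects in Section 17 by the 130 expected subjects to size the loss. The documents do not support that: the count is for hypoglycemia needing another person's help and states no altered-consciousness condition, whereas the Section 16.5 definition requires one.

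No test, significance level, power figure or sample size is affected.

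**What to change.** 1. In Section 18, change 6 days to 7 days after checking against the sensor label. If the label says 6, correct footnote 8 of Section 11.3 instead.
2. In Section 16.5, delete symptoms as a condition for recording, so that every event meeting the diagnostic criteria is entered as a DKA adverse event. Send events that meet only the pH or only the bicarbonate criterion to the DSMB for adjudication. Do not word this so that the Section 19.2 enrollment pause applies only when both criteria are met; that would weaken a safety rule for the sake of tidiness.
3. The sponsor should decide which severe hypoglycemia rule is meant and state it identically in Section 18, Section 19.1 and the synopsis.

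The cost is protocol wording, a matching note in the adverse event eCRF guidance and one line in the DSMB instructions. No visits, samples or data are added.

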16.6. Definitions and Classification of Adverse Events

Medtronic uses the definitions provided in ISO 14155:2011 and 21 CFR 812 for adverse event definitions. Where the definition indicates “device”, it refers to any device used in the study. This might be the device under investigation, or any market released component of the system.

The term “investigational device” is part of ISO14155 definitions. The term “investigational device” refers to any device used in the study including market released devices.

Adverse Event (AE) (ISO14155-2011)

Any untoward medical occurrence, unintended disease or injury, or untoward clinical signs (including abnormal laboratory findings) in subjects, users or other persons, whether or not related to the investigational medical device.

- Note 1: This definition includes events related to the investigational medical device or the comparator.
Note 2: This definition includes events related to the procedures involved.
Note 3: For users or other persons, this definition is restricted to events related to investigational medical devices.

Adverse Device Effect (ADE) (ISO 14155-2011)

Adverse event related to the use of an investigational medical device.

Note 1: This includes any adverse event resulting from insufficiencies or inadequacies in the instructions for use, the deployment, the implantation, the installation, the operation, or any malfunction of the medical device.

Note 2: This includes any event that is a result of a use error or intentional misuse of the investigational device.

Serious Adverse Event (SAE) (ISO 14155-2011)

An adverse event that

- Led to a death
- Led to a serious deterioration in the health of the subject, that either resulted in
 - life threatening illness or injury,
 - a permanent impairment of a body structure or a body function
 - in-patient* or prolonged hospitalization, or
 - medical or surgical intervention to prevent life-threatening illness or injury or permanent impairment to a body structure or a body function
- Led to fetal distress, fetal death or a congenital abnormality or birth defect

**Inpatient Hospitalization is defined as: 24 hour acute admission to the hospital based on urgent medical need rather than elective admission.*

Note 1: A planned hospitalization for pre-existing condition, or a procedure required by the CIP, without a serious deterioration in health, is not considered to be a serious adverse event.

Note 2: The term "life-threatening" in the definition of "serious" refers to an event in which the patient was at risk of death at the time of the event; it does not refer to an event which hypothetically might have caused death if it were more severe. (ICH Topic E 2 A Clinical Safety Data Management: Definitions & Standards for Expedited Reporting. EMEA 2006)

Serious Adverse Device Effect (SADE) (ISO 14155-2011)

Adverse device effect that has resulted in any of the consequences characteristic of a serious adverse event

Unanticipated Adverse Device Effect (UADE) (21 CFR 812.3(s)) equivalent to USADE (ISO14155-2011 3.42)

Any serious adverse effect on health or safety or any life-threatening problem or death caused by, or associated with, a device, if that effect, problem, or death was not previously identified in nature, severity, or degree of incidence in the investigational plan or application (including a supplementary plan or application), or any other unanticipated serious problem associated with a device that relates to the rights, safety, or welfare of subjects.

